Comparing two dry needling interventions for plantar heel pain: a protocol for a randomized controlled trial

Clinical Trials: NCT03236779

Author: [name]

DATE: 23-1-2021

COMPARING TWO DRY NEEDLING INTERVENTIONS FOR PLANTAR HEEL

PAIN: A RANDOMIZED CONTROLLED TRAIL

Relevant scientific background

Plantar heel pain (PHP) is a common problem affecting the foot, causing soreness or tenderness in the sole of the foot, and under the heel, sometimes extending into the medial arch. The frequency and incidence of PHP is uncertain, however it is estimated that over the course of a lifetime 10% of the population may suffer from this condition.²³ Several pathologies may cause PHP, such as myofascial pain syndrome, plantar fasciitis or heel spur, amongst others.⁴ The clinical diagnosis is usually established based on the patient's history and physical examination, including pain during the first steps in the morning or after prolonged rest, as well as pain during prolonged standing or walking.^{2 3 5} The identification of the main cause of pain can be challenging as this is often multifactorial.⁶ and despite its prevalence, the etiology of PHP is not well understood.² The presence of myofascial trigger points (MTrPs) within the muscles of the foot and lower leg may play an important role in people in PHP,⁷ an implicit assumption underlying many recent studies.⁸-¹¹ In addition, there is a lack of consensus regarding the ideal management approach for PHP. ¹²⁻¹⁴ Clinical practice guidelines support the use of conservative treatment, such as joint and soft tissue mobilization or self-stretching home programs.^{2 3} In particular, self-stretching home programs have shown to be effective for addressing PHP. ²⁶¹⁵ Furthermore, recent randomized clinical trials (RCTs) have shown that there is an additional effect of reduction of pain severity when selfstretching home programs are combined with ischemic compression¹¹ and with dry needling.⁹ Physical therapy approaches continue to evolve and include the combination of dry needling and electrolysis, known as percutaneous needle electrolysis, with promising results for the treatment of tendon pathologies. 16-18 The percutaneous needle electrolysis technique is a minimally invasive

treatment that consists of the application of a galvanic electrolytic current that causes a controlled local inflammatory process in the target tissue. This promotes phagocytosis and the subsequent regeneration of the affected tissue. ¹⁶ ¹⁷ Currently, percutaneous needle electrolysis is being used in clinical practice to manage MTrPs, however, there are no studies supporting any additional beneficial effects of the same over dry needling.

From a biological point of view, it seems reasonable to hypothesize that subjects may display improvements thanks to the mechanical effects of the needle, and that patients may experience superior benefits when the electrolysis effect is added to the mechanical stimulus provided by the needle. Therefore, the aim of this RCT was to compare the effectiveness of dry needling versus percutaneous needle electrolysis for improving the level of pain, function and quality of life of patients suffering from PHP caused by MTrPs.

METHODS

Design

This study was a prospective, parallel-group RCT with blinded outcome assessment. Participants were recruited from Kuwait City, Kuwait, and both the assessment and intervention were conducted at the Physical Medicine and Rehabilitation Hospital in Kuwait. The study was conducted in compliance with the Helsinki Declaration of Human Rights and ethical approval was obtained by the Medical Ethics Committee of the State of Kuwait Ministry of Health, with reference number 642/2017. The study protocol has been previously published¹⁹ and the trial is registered at Clinicaltrials.com, number NCT03236779. This RCT was reported in accordance with the CONSORT statement for non-pharmacological trials.

Participants

The study subjects were male and female adults, enrolled at the Physical Therapy Department of the Physical Medicine and Rehabilitation Hospital in Kuwait City. Participants were included if they fulfilled the following criteria: 1) diagnosed of plantar heel pain in accordance with the Clinical Guidelines linked to the International Classification of Function, Disability and Health from the Orthopedic Section of the American Physical Therapy Association;²³⁸⁹ 2) aged 21 to 60 years at admission to the study, according to the Kuwaiti Ethical Committee; 3) a history of PHP for over one month, showing no improvements with previous conservative treatment; 4) the ability to walk 50 meters without any support; 5) the presence of MTrPs on plantar and calf muscles based on an initial physical examination carried out by a physiotherapist (MA) with experience and training in MTrPs; 6) accepting treatment from a male physiotherapist; 7) the ability to understand the study and the informed consent, as well as having signed the consent form.

The exclusion criteria were: 1) needle phobia; 2) needle allergy or hypersensitivity to metals; 3) the presence of coagulopathy or use of anticoagulants according to medical criteria; 4) the presence of peripheral arterial vascular disease; 5) pregnancy; 6) dermatological disease affecting the dry needling area; 7) the presence of any chronic medical condition which might preclude participation in the study, such as: malignancy, systemic inflammatory disorders (e.g., rheumatoid arthritis, psoriatic arthritis, ankylosing spondylitis, septic arthritis), neurological diseases, polyneuropathy, mononeuropathy, and sciatica; 8) treatment of plantar heel pain with needling or acupuncture during the last four weeks; 9) history of injection therapy in the heel over the previous three months; and 10) previous history of foot surgery or fracture. Receiving or implementing any form of treatment for the plantar heel pain (taping, night splints, massage therapy or footwear modifications) during the trial was considered withdrawal criteria.

The sample-size calculation initially estimated that 39 participants per group would provide 80% power to detect a minimally important difference of 13 points in the pain domain of the Foot Health Status Questionnaire with a standard deviation of 20 points²⁰ and an alpha risk at 0.05. Allowing for a 20% loss to follow-up, a minimum of 47 participants was required in each group, equaling 94 participants in total. Based on initial data collection, the drop-out rate was recalculated to be 25% and the sample size was therefore increased to a total of 102 patients.

Patient and public involvement

No patients were involved in the design, recruitment or conduction of this study and the burden of the intervention was not assessed by patients themselves neither.

Randomization

Participants who fulfilled the inclusion criteria received standardized oral and written information, and, after consenting to participate in the trial, they were randomized using block randomization by blocks of 10 patients. Allocation was randomly assigned using a computer program (Randomizer, https://www.randomizer.org/) with random patient file number sequences generated by a third person not involved in the study.

Procedure and interventions

Two study groups were randomly formed. The first was treated with dry needling whereas the second group was treated with percutaneous needle electrolysis. In both groups, during the first session, all participants were taught a self-stretching protocol¹¹ which has been demonstrated to be effective for the management of PHP,²⁶¹¹ consisting of self-stretching of the calf muscles and

specific self-stretching for the plantar fascia.¹⁹ The frequency of calf and plantar fascia-specific self-stretching exercises was twice a day, using intermittent stretching lasting 20 seconds, followed by 20-second rest periods, for a total of three minutes per stretch.¹¹ Compliance with the selfstretching protocol was registered before each treatment session and at the four-week follow-up. The muscles considered for invasive physical therapy treatment were the soleus, gastrocnemius, quadratus plantae, flexor digitorum brevis and abductor hallucis. These muscles typically refer pain to the heel and are muscles than can be directly palpated or that can be needled precisely and safely without ultrasound guidance. The clinician performed a physical exam to find MTrPs following the criteria by Travell and Simons: 1) the presence of a taut band and 2) identification of an exquisite spot tenderness or a nodule.⁷ A flat palpation or pincer palpation technique was used to palpate the MTrPs, depending on the muscle being assessed. If a muscle contained more than one MTrP, the most sensitive MTrP was treated, according to the patient's perceived pain upon palpation. If the patient presented bilateral pain, the clinician treated both sides. The patient's position (supine, prone or lateral decubitus position) depended on each muscle examined and was the same for the assessment as well as for the intervention.

Each participant received four individual physical therapy sessions, once a week. Participants was treated by one physical therapist registered at the Kuwait Ministry of Health (ZA) with five years of practical experience in the field of dry needling and appropriate training in the protocol. The duration of each session was approximately 30 minutes.

Participants were instructed to use the appropriate dose of medication as prescribed by their Physical Medicine and Rehabilitation physician (analgesics and non-steroidal anti-inflammatory medications) and were required to report any changes to the assessor during the evaluations if they took any additional medication or underwent any treatment during the intervention.

Invasive Intervention Groups: Dry Needling and Percutaneous Needle Electrolysis

Specific needles for dry needling were used during invasive treatments (Agu-punt, Spain). Needle length was determined by the location of the MTrP and ranged from 30 to 75mm in length (or longer if necessary, according to the patients' characteristics). The diameter of the needle was 0.25-0.30 mm. If the participant was sensitive to the needle insertion, the level of manipulation was reduced. If this measure proved insufficient for reducing the painful stimulus, needle manipulation ceased altogether and the needle was left in situ.^{21 22}

To maintain appropriate hygienic conditions during the invasive treatments, the clinician wore latex gloves and thoroughly cleaned the skin of the area to be needled with an antiseptic solution (70% Propan-2-ol, Skin-des). Upon removal of the needle, the area was firmly compressed for 10 seconds. The needle was discarded after each single use. In both groups, the intervention was terminated in the case of severe adverse effects and if the participant did not wish to continue.

Dry Needling Arm

Once the clinician located the MTrP, the needle was inserted over the same and a rapid needle entry was performed. The chosen technique for manipulating the needle was the technique described by Hong, which consists of a rapid needle entry and exit (fast in/fast out), in order to obtain a local twitch response, lasting 5 seconds employing a rhythmic movement at approximately 1Hz/sec (5 entries).

Percutaneous Needle Electrolysis Arm

The electrotherapy equipment used (Physio Invasiva, PRIM Fisioterapia, Spain) produced a

continuous galvanic current through the cathode while the patient held a hand-held anode. ¹⁸ Once the needle reached the relevant treatment area, this was needled in exactly the same manner as in the dry needling group, with the only difference being that the needle was transmitting an electrical current with an intensity of 1.5 mA (intensity was adapted to patient's characteristics according to their pain tolerance).

Study Variables

An independent assessor (MA) blinded to treatment group allocation conducted all assessments at baseline, and at the 4, 8, 12, 26 and 52-week follow-up. Demographic and disease data were collected at baseline.

The primary outcome was the Foot Pain domain of the Foot Health Status Questionnaire (FHSQ), a validated measure of foot-health status²³ that has been used in similar trials, which evaluated the effectiveness of different interventions for plantar heel pain. ⁸ ²⁴ ²⁵ Individual item scores were inserted into a computer program (FHSQ V.1.03) which, after data transformation, provides a score ranging from 0 to 100 for each domain, ²⁶ with greater scores reflecting a better condition. ²⁷ Secondary outcomes were the Foot Function, Footwear and General Foot Health domains of the Foot Health Status Questionnaire, as well as the average and maximum level of pain over the past 48 hours using the visual analogue scale (VAS). Participants were explained that a score of 0 indicated the absence of pain whereas a score of 10 represented the maximum tolerable pain. Additionally, before each treatment session, they were asked to complete the VAS and after each treatment session, participants were asked to score their current pain immediately upon standing up and walking a few steps. The VAS is widely used and is both valid and reliable. ²⁸⁻³⁰

Quality of Life (QoL) was assessed with the EQ-5D-5L, which was completed by the participants at baseline and at the 4, 8, 12, 26 and 52-week assessments. The EQ-5D-5L self-report questionnaire is a descriptive system with five questions, each representing one dimension of Health-related Quality of Life, i.e. mobility, self-care, daily activities, pain/discomfort and depression/anxiety. Each dimension can be rated on five levels: no problems, slight problems, moderate problems, severe problems and extreme problems. Together, the results serve to classify people into 1 of 3125 possible health states.³¹ These health states are subsequently transformed to quality of life values with the EQ-5D-5L crosswalk value sets.³²

Statistical Analysis

The statistical analysis was performed using IBM SPSS Statistics (version 25, IBM, Chicago, IL) by intention to treat, with the last observation carried forward. The investigator who performed the analyses was masked to group allocation. The significance level for all statistical tests was set at $P \le 0.05$.

Chi-squared tests were used to analyse if there were differences in categorical variables between groups at baseline. In addition, independent Student's t-tests and Mann-Whitney U tests were used for parametric and nonparametric quantitative variables, respectively. Chi-squared tests were used to evaluate the compliance of the self-stretching protocol.

Following recommendations to estimate treatment effects in RCTs, linear mixed models adjusted for baseline values were used to test the mean effect of treatment interventions at the follow up at the 4, 8, 12, 26 and 52-week follow-up, for the Foot Health Status Questionnaire and EQ-5D-5L measures. Linear mixed models adjusted for baseline values were used to test the mean effect of treatment interventions at the second session, third session, fourth session, and at the 4, 8, 12, 26

and 52-week follow-ups, for measures of VAS (average and maximum). Individual repeated measures (RM) ANOVAs were used to test time effects within each treatment group for primary and secondary outcomes. Cross-sectionally, at all linear mixed models and RM-ANOVAs, the Bonferroni correction was used to test between-group time point differences or within-group time changes, respectively. The Greenhouse-Geisser correction was applied for correcting against violations of sphericity, whereas eta-squared (η^2) was used to estimate the magnitude of the difference between both groups (0.01 small effect, 0.06 medium effect and 0.14 large effect).³³ Independent t-tests were used to determine any difference between groups for measures of level of pain immediately after each treatment session.

REFERENCES

- 1. Landorf KB. Plantar heel pain and plantar fasciitis. BMJ Clin Evid 2015;2015:1111.

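### Other heel treatment triggers withdrawal with no provision for continued assessment, so obtainable week 8 to 52 scores are replaced by carried-forward values

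*Combined protocol and SAP*

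**What the plan says.** All references are to the combined protocol and SAP.

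- **Participants**, last sentence of the eligibility text: receiving or using "any form of treatment for the plantar heel pain (taping, night splints, massage therapy or footwear modifications) during the trial was considered withdrawal criteria". It does not say whether withdrawal is from needling, from follow-up or from both. No other section says that withdrawn participants continue to be assessed.
- **Procedure and interventions**: "Each participant received four individual physical therapy sessions, once a week". Home stretching is the other component, and compliance with it is logged only up to the week-4 visit.
- **Study Variables**: the blinded assessor "conducted all assessments at baseline, and at the 4, 8, 12, 26 and 52-week follow-up".
- **Procedure and interventions**, on reporting: participants "were required to report any changes to the assessor during the evaluations if they took any additional medication or underwent any treatment during the intervention". No consequence is attached to such a report.
- **Statistical Analysis**: the analysis is "by intention to treat, with the last observation carried forward". For the foot health questionnaire and EQ-5D-5L, "linear mixed models adjusted for baseline values were used to test the mean effect of treatment interventions at the follow up". No sensitivity analysis for missing data is given.
- **Participants**, sample size: "Based on initial data collection, the drop-out rate was recalculated to be 25" per cent, with the total raised to 102. Reasons for drop-out are not broken down.

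**The concern.** An intention-to-treat comparison that disregards other treatment is legitimate, but it needs the scores measured after that treatment began. On its plain reading the withdrawal rule removes those scores from people who could still have attended.

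Take a participant who starts a night splint at week 10. They leave the trial and enter weeks 12, 26 and 52 with their week-8 score. The gap is created by the protocol, not by the participant, and it is unlikely to be random: people look for other treatment when pain persists, and everyone enrolled had already failed to improve on conservative care.

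At stake are the late between-group differences. Early scores stand in for late ones, possibly more often in one arm than in the other, and an early difference that has since disappeared can be carried to week 52.

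**Working it through.** **1. Inputs and the plan's own figure.** From the sample-size text: difference 13, SD 20, alpha 0.05 (two-sided assumed), power 80%.

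n per group = 2 × (1.96 + 0.84)² × 20² / 13² ≈ 37.1, so 38 by the normal approximation. The t-based solution is 38.14, so 39, as stated. The inputs 13 and 20 are therefore safe to reuse.

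**2. What is left to withdraw from.** Four weekly sessions occupy about weeks 0–4. That leaves 52 − 4 = 48 of 52 weeks (92%) and four of the five follow-up visits (8, 12, 26, 52) after needling. Apart from home stretching, withdrawal in that period removes only assessments.

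**3. How many could be affected.** Drop-out from all causes is 0.25 × 102 = 25.5, about 26 participants. The part due to other treatment is not given. A range of 5% to 25% is assumed, the top being the whole planned drop-out.

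**4. Direction of bias.** Ignoring baseline adjustment, let p be the share carried forward in an arm, and d the mean carried score minus the mean score those people would have had at week 52. Then

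bias in (better − worse) = p_better × d_better − p_worse × d_worse.

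Higher scores are better, and the worse arm is expected to have the larger p.

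- If withdrawal follows a recorded poor score, the carried value is selected to be low, so d < 0 and the difference is overstated.
- If it follows pain that arises after the last recorded score, the carried value is too good, so d > 0 and a lasting difference is understated.

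The week-10 splint fits either case.

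**5. Illustration of size.** Simulation: baseline plus five visits, SD 20, equal correlation 0.3, 0.5 or 0.7 between visits, 200,000 per arm. A participant withdraws at the first score below a threshold, with the score taken exactly or with noise of SD 20. The threshold gives 5, 12.5 or 25% withdrawn overall. Later scores are carried forward and week 52 is analysed adjusting for baseline. Other treatment is assumed to have no effect of its own. The standard error of a simulated difference is about 20 × √(1 − 0.5²) × √(2/200,000) ≈ 0.055, so the ends of ranges can move by about 0.1 between runs.

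Lasting 13-point difference, withdrawal after a recorded poor score, LOCF estimate at week 52 (5 / 12.5 / 25% withdrawn):

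| Correlation | No noise | With noise |
|---|---|---|
| 0.3 | 15.2 / 16.8 / 17.9 | 14.3 / 15.0 / 15.7 |
| 0.5 | 14.5 / 15.8 / 16.3 | 13.8 / 14.5 / 14.8 |
| 0.7 | 14.0 / 14.6 / 14.9 | 13.5 / 13.8 / 14.1 |

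At correlation 0.5, no noise and 25% overall, the arms lose 36% and 14%.

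Ranges over all settings, allowing for repeat runs:

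| Truth | Trigger | LOCF | Observed-score likelihood model |
|---|---|---|---|
| Lasting 13 | recorded poor score | about 13.4–18 | 13.0–13.1 (correlation 0.5) |
| Lasting 13 | pain at the next, unrecorded visit | about 11.3–12.9 | about 9.5–12.8 |
| Faded (13, 13, 6.5, 0, 0) | recorded poor score | about 0.6–3.6 | −0.02 to 0.12 (correlation 0.5) |
| Faded | pain at the next, unrecorded visit | about 0.3–2.1 | about −0.5 to 0.04 |

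**6. Boundary checks.** With no difference at any visit, the LOCF bias is 0 within simulation error. With withdrawal unrelated to pain, a lasting 13 stays at 13.0–13.1. A faded difference still leaks: if a share p is carried from week 4 or 8 regardless of pain, week 52 shows 13p, that is 13 × 0.05 = 0.65 to 13 × 0.25 = 3.25 points.

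**The case against.** **Withdrawn participants may have been assessed anyway.** The text is silent and does not say that assessment stops. A separately published protocol is cited and may define withdrawal, but it is not among these documents. This stands as a caveat: if those scores were collected and used, the problem disappears and one sentence settles it. It does not cure the present text.

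**A reader might infer that a lasting difference is overstated.** The documents do not support a direction. Step 4 shows that it depends on whether the pain prompting other treatment had already been recorded, which the plan cannot tell us.

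**A reader might attribute the 25% drop-out to other treatment.** Nothing does so. At 5% withdrawn with noise, the recorded-score case is off by only 0.5 to 1.3 points against a 13-point target.

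**A reader might infer that extra painkillers also trigger withdrawal.** The text points the other way. The examples in the rule are all physical measures, prescribed analgesics and anti-inflammatories are allowed, and additional medication carries only a duty to report.

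**The reporting window limits the rule's reach.** If the reporting period means only the four treatment weeks, the plan has no stated way to learn of a week-10 splint. The rule would then seldom act late and most later scores would be measured. If reporting runs to week 52, the rule acts all year. Late use going unrecorded and late scores being lost are therefore alternatives, not harms to be added together.

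**The remedy is not neutral.** When withdrawal follows unrecorded pain, the observed-score model is further from a lasting 13 than LOCF. This stands, and it is why continued assessment comes first in the fix.

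**Conclusion.** The concern holds as a design fault without a known direction. Followed as written, the plan discards week 8–52 scores that could be obtained and that its intention-to-treat label requires, probably from participants with persistent pain, and replaces them by LOCF.

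The conclusion rests on reading withdrawal as ending assessment, which is the plain reading but is not stated. The size rests on assumed withdrawal rates, correlations and triggers, so the simulated figures show how far and in which directions the week-52 result could move; they do not estimate what happened. The fault is worth correcting because the change is cheap and a faded difference can appear to persist under either trigger. Confidence is medium.

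**What to change.** 1. **Participants:** replace the withdrawal criterion with wording such as: *Other heel treatment is recorded; it may end needling but does not end follow-up, and the participant is assessed at all remaining visits and these scores are analysed.*
2. **Procedure and interventions:** ask about other treatment since the previous assessment, at weeks 4, 8, 12, 26 and 52.
3. **Statistical Analysis:** make the planned baseline-adjusted mixed model, fitted to observed scores, the primary analysis and keep LOCF as a sensitivity analysis. For participants already withdrawn, the model assumes data missing at random and targets the effect had they not used other treatment. It may understate a lasting effect if that assumption fails. So add a sensitivity analysis for data not missing at random, for example lowering the model-based later scores of those withdrawn for other treatment by amounts up to the plan's 13 points, separately in each arm.
4. **Reporting:** tabulate by arm and visit the number withdrawn for other treatment and their last scores before withdrawal.

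Cost: two sentences, one fixed question per visit, one table, one added sensitivity analysis, and up to four more assessments for each participant kept in follow-up. No extra participants are needed. With step 1 the comparison includes the effect of other treatment, so the difference will be smaller if the worse arm uses more of it and it works. If data collection is over, only steps 3 and 4 can still be applied.

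### Does the miscalculated 20% loss allowance (47 per group rather than 49) leave the trial short of its stated 80% power?

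*Combined protocol and SAP*

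**What the plan says.** The sample-size text is the paragraph in the Participants section that follows the eligibility criteria. It gives three figures in order.

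- **Before losses:** "The sample-size calculation initially estimated that 39 participants per group would provide 80% power". The inputs are "a minimally important difference of 13 points in the pain domain of the Foot Health Status Questionnaire", "with a standard deviation of 20 points" and an alpha of 0.05.
- **Initial allowance for loss:** "Allowing for a 20% loss to follow-up, a minimum of 47 participants was required in each group, equaling 94 participants in total".
- **Revision:** after early data collection, "the drop-out rate was recalculated to be 25% and the sample size was therefore increased to a total of 102 patients".

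No inflation formula is printed, and the paragraph does not say whether the second and third figures start from the rounded 39 or from an unrounded value. The Statistical Analysis section adds that the analysis is "by intention to treat, with the last observation carried forward", so participants lost to follow-up stay in the analysed set.

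**The concern.** An allowance for loss should be made by dividing the required number by the share expected to remain. Multiplying by one plus the loss rate always gives too few, and 47 is exactly what multiplication gives from 39. The text presents 47 as a required minimum, yet 47 with 20% loss does not leave the 39 that the same paragraph ties to 80% power.

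The next figure adds to the doubt. From 39, neither rule gives 102: dividing gives 104 and multiplying gives 98. The two steps therefore seem not to share a rule and a base. This paragraph is the trial's only power justification. If its arithmetic were wrong in a way that reached the enrolled number, the trial could be smaller than its own target requires.

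**Working it through.** **Inputs (sample-size paragraph, Participants).** Difference 13, SD 20, alpha 0.05, power 80%, 39 per group, loss 20% and then 25%, totals 94 and then 102. Assumed because not stated: a two-sided test, equal allocation and equal loss in both arms. The two-sided reading is supported by the result, since a one-sided test would need only 30 per group.

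**Step 1: reproduce 39.** The standardised difference is 13/20 = 0.65.

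- Normal approximation: 2 × [20 × (1.960 + 0.842)/13]² = 37.15 per group.
- Two-sample t-test (noncentral t): 38.14 per group. Power is 79.9% at 38 and 80.9% at 39, so 39 is reproduced.

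**Step 2: the 20% allowance.**

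- Multiplying: 39 × 1.20 = 46.8, so 47 per group and 94 in total. This matches the plan.
- Dividing: 39/(1 − 0.20) = 48.75, so 49 per group and 98 in total.
- Left from the stated figure: 47 × 0.80 = 37.6 per group (94 × 0.80 = 75.2, against 78 needed).
- Loss that 47 can absorb while keeping 39: 1 − 39/47 = 17.0%.

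**Step 3: what that costs in power.** At 37.6 per group the t-test has 79.4% power (80.5% by the normal approximation). The deficit against the 80% target is 0.6 percentage points, and 38.14 − 37.6 = 0.54 patients per group. The gap to the 80.9% at 39 is 1.5 points, but 0.9 of that is surplus from rounding up.

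**Step 4: the operative figure, 102 (51 per group).**

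| Check | Calculation | Result |
|---|---|---|
| Against the proper figure at 20% loss | 102 vs 98 | 4 above |
| Left at 25% loss | 51 × 0.75 | 38.25 per group (76.5 in total) |
| t-test power at that number | 38/38; 38.25; 38/39 | 79.9%; 80.1%; 80.4% |
| To keep a full 39 at 25% loss | 39/0.75 = 52 | 104, two more than 102 |
| Loss at which 51 still keeps 39 | 1 − 39/51 | 23.5% |
| From the unrounded t-test number | 38.14/0.75 = 50.85 → 51 | 102, as stated |

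The 102 is therefore what correct division gives from the unrounded requirement.

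**Step 5: can one rule and base give both 47 and 51?** Not from 39. Some nearby bases do: 37.55/0.80 = 46.94 → 47 and 37.55/0.75 = 50.07 → 51, rounding up. Division from 38 gives 47.5 and 50.67, which become 47 and 51 if rounded to nearest with the tie taken down. So the pair of figures does not prove inconsistent methods. It shows only that the base is not written down.

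**The case for a change.** The strongest case for a correction is that 94 stands in the current text as a required minimum, and on the plan's own inputs it is not one. That holds however 47 was reached, because 47 × 0.80 = 37.6 is below 39. The next sentence does not repair it either. It puts the whole rise to 102 down to the new drop-out rate, although the step from 94 to 98 was already needed at 20%. A correction would take one or two sentences and no extra patients. Carrying the last observation forward is no rescue, since imputed values do not restore the information lost and the paragraph itself chose to allow for loss.

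All of this stands as arithmetic, but it does not justify a change.

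- The paragraph is a history in the past tense of what was first planned and then revised. Rewriting 94 as 98 would record an initial target that the document does not say was ever set.
- Stating the base behind 102 would be tidy, but that number already delivers the stated power.
- Saying which analysis set the power claim covers is a reporting preference, separate from this slip.
- A deficit of 0.6 points is finer than the calculation can resolve. The Statistical Analysis section uses baseline-adjusted mixed models, not an unadjusted t-test. In a simple covariance-adjusted approximation, power at 37.6 per group is 80.0% with an assumed baseline correlation of 0.12 and 83.0% with 0.3 (the documents give no value). The Bonferroni correction across time points pulls the other way.

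**Conclusion.** The slip is real but has no effect. The initial allowance should have been 49 per group (98) on the stated inputs, not 47 (94). That is a shortfall of 4 patients and 0.6 percentage points against the 80% target. The multiplication route is inferred from the match, since no formula is shown.

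The figure that governs the trial is 102. It exceeds 98 and gives about 80% power at 25% loss (79.9% to 80.4%, depending on how the half patient is counted). The two patients separating it from 104 are a rounding matter.

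These results assume a two-sided unadjusted t-test at one time point, equal allocation and equal loss, with power counted on participants who have observed outcomes. Nothing the trial enrols, tests or estimates would differ if the paragraph were reworded, so the plan can stand. A reader who wants the trail can note that the 94 was too low and was superseded, and that 102 keeps about 38 rather than 39 per group.
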